Most maternal deaths occur immediately around childbirth³ and approximately 45% in the first 24 hours.⁴ As such, the promotion of facility-based childbirth has been a corner stone of strategies to reduce maternal and neonatal deaths in low and middle-income countries.^{5,6} However, despite increases in the proportion of women delivering at facilities, reductions in mortality and morbidity have not been as rapid as expected.⁵ Evidence points to delays at the facility in the recognition of complications and timely intervention as once cause of morbidity and mortality.⁷⁻¹² Recognizing the critical timeframe in the immediate postpartum period, current guidelines from WHO call for close monitoring during this time.¹³ Similarly, nursing standards in resource-rich settings recommend physiologic monitoring every 15 minutes for the first 2 hours postpartum, then every fours for the first 24 hours.^{14 15} Sustaining such high frequency monitoring remains a challenge even in resource-rich settings.^{16 17} In RLS contexts such as Mbarara, Uganda, where staff-to-patient ratios may be as high as 1:50,¹⁸ such normative standards around monitoring are unattainable with current systems of physiologic monitoring.

Abnormalities in physiologic signs have been shown to predict subsequent in-hospital mortality and morbidity amongst emergency department and medical ward patients.¹⁹⁻²³ In response to these findings, health care systems in resource-rich settings have introduced “Track and Trigger” protocols and “Early Warning Scores” to identify abnormalities in physiologic signs and activate appropriate responses.²⁴ In the case of heart disease, combining early warning of potential illness with

appropriate medical response has reduced rates of cardiac arrest, readmissions to critical care, and mortality.²⁵⁻²⁷ Similar strategies have been recommended in an obstetric setting, where the most common causes of mortality are hemorrhage, hypertensive disease, and sepsis, accounting for 27.1%, 14.0% and 10.7% of maternal deaths worldwide.²⁸ These conditions are commonly associated with abnormal physiologic signs—hemorrhage causing tachycardia and hypotension; pre-eclampsia/eclampsia causing hypertension and hypoxia; and sepsis causing fever, tachycardia, hypotension, and hypoxia.^{29,30}

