The wireless monitor to be used is a wearable wireless vital sign monitor called Current™. The device provides continuous real-time transmission of oxygen saturation, respiration rate, pulse rate, temperature, motion and activity, and posture captured every 2 seconds. It is integrated with the Omron Evolv blood™ pressure cuff to allow automated capture of blood pressure. Physiologic data from the sensor is transmitted via WiFi to a secure cloud storage (hosted by Amazon Web Services). Current™ is fully HIPAA¹ compliant and HITRUST² certified and has received US FDA approval. Physiologic data can then be accessed via a secure password protected mobile phone app or displayed on a monitor for real-time viewing. Pre-defined criteria can be used to program alerts or notifications should vital signs fall outside of the range. These notifications can be received via SMS or a mobile app notification. Notifications can be sent to multiple providers at a time. Providers can also log on or off from the device corresponding to their duty shifts.

To complete Aim 1, we will enroll all willing attending doctors and staff midwives with clinical duties covering the maternity ward, emergency cesarean delivery and postoperative care during the study period to use the wireless physiologic system and receive message alerts. Due to staffing the numbers of clinicians may fluctuate during the enrollment period. We will also enroll 1235 women undergoing emergency cesarean delivery during the study period during intervention blocks to wear a wireless physiologic monitor for 24 hours after birth. An additional 1235 women, also undergoing emergency cesarean during the study period during non-intervention blocks, will form a control group and have medical record review only. *We request to waive consent for this record review only.* Clinicians and peripartum women participating in wireless physiologic monitoring will form the same participants for Aim 2, which will involve participant observation, record review, and retrieval of data from the wireless monitoring system and clinician responder phones. To complete Aim 3, We will perform semi-structured interviews on 30 clinicians and 30 postpartum women drawn from

¹ HIPAA: Health Insurance Portability and Accountability Act of 1996) is United States legislation that provides data privacy and security provisions for safeguarding medical information

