11. Every 24 hours a research assistant will perform medical chart review on enrolled participants to assess for documentation of the occurrence of any severe maternal outcome (Table 2). The research assistant will also review daily 24-hour reports generated by covering clinicians (standard maternity ward practice) to identify potential severe maternal outcomes not documented in the medical record.

Table 2: Severe Maternal Outcomes based on WHO Near Miss Criteria with demonstrated feasibility of collection in a RLS^{28,29,71}

Outcome	Definition/Measurement
Death	Mortality occurring at any time point after delivery and prior to discharge
Clinical based near-miss criteria	
Acute cyanosis	Blue or purple coloration of the skin or mucous membranes due to low oxygen saturation
Gasping	Terminal respiratory pattern, the breath is convulsively and audibly caught.
Severe bradypnea or tachypnea	Respiratory rate < 6 or Respiratory rate > 40
Shock	Persistent systolic BP ≤ 80 mmHg or a persistent systolic BP ≤ 90 mmHg with a HR ≥ 120.
Oliguria	Urinary output < 30 ml/hour for 4 hours or < 400 ml/24 hours non-responsive to fluids/diuretics.
Failure to form clots	Bedside clotting test or absence of clotting from the IV site after 7 minutes
Prolonged unconsciousness	Complete or near-complete lack of responsiveness to external stimuli.
Cardiac arrest	Sudden absence of pulse and loss of consciousness.
Stroke	Neurological deficit of cerebrovascular cause persisting ≥ 24 hours.
Uncontrollable fits	Refractory, persistent convulsions or status epilepticus.
Total paralysis	Complete or partial paralysis of both sides of the body.
Jaundice in the presence of pre-eclampsia	BP > 140/90) with proteinuria (> 1 + dipstick in ≥ 2 samples) and jaundice.
Laboratory-based near miss criteria	
Acute severe azotemia	Creatinine > 300 mmol/l or > 3,5 mg/dl
Severe acute hyperbilirubinemia	Bilirubin > 100 µmol/l or > 6.0 mg/dl.
Severe acute thrombocytopenia	<50 000 platelets/ml
Management-based near-miss criteria	
Use of continuous vasoactive drugs	Uninterrupted infusion of dopamine, epinephrine, or norepinephrine.
Hysterectomy	Surgical removal of the uterus following infection or hemorrhage.
Massive transfusion	Transfusion of ≥ 5 units of blood
Intubation and ventilation not related to anesthesia	Placement of an endotracheal tube or ventilation for > 60 minutes purposes other than anesthesia
Dialysis for acute renal failure	

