On average approximately 8-10 emergency cesarean deliveries are performed at MRRH daily. Thus, in a two week block we estimate ~ 112 emergency cesareans performed. We plan to capture all women delivered by emergency cesarean during an intervention block thus minimizing the risk of selection bias based on the severity level. Assuming 85% of women consent to participation (conservative estimate based on >90% recruitment in prior studies)^{5,74,75}, this yields an estimated 95 women per block. Over 12 months of enrollment, we will therefore have 13 intervention blocks and 13 control blocks. This yields an estimated 1,235 women in the intervention group and 1,235 in the control group. Assuming an intraclass correlation coefficient of 0.01, the effective sample size after taking account of clustering is 633 per group. This will allow us to detect a difference of 5.7% in the SMO rate between the two study arms, with a two-sided significance level of 0.05, and 80% power, assuming a baseline rate of SMO of 13% ^{71,73}

Risk/Discomforts and protections

Clinicians:

- Risk of false alerts, alert fatigue: Clinicians will be asked to hold a mobile phone and respond to alerts. It is possible that alerts of physiologic sign abnormalities may not correspond to a developing or established clinical abnormality and in responding to the alert clinicians may become fatigued from alerts. Study investigators will monitor for this occurrence and the impact on clinician performance and duties and adjust study protocols as necessary
- Risk of diversion and interruptions to work on other patients: Alerts sent to clinicians may also prompt them to perform additional exams or clinical procedures that may or may not be beneficial to the patients from which alerts were received. This may divert attention or human resource away from other clinical needs. We will monitor for any diversions resulting in substandard clinical care. If these occur we will consider protocol modifications. Any safety concerns or adverse events arising because of false alerts or diversions will be communicated to the IRB within 10 days.

Peripartum women:

- Theoretical risk of exposure to radio emissions from Wi-Fi from the biosensor: There is a theoretical risk of exposure to Wi-Fi signals from the biosensor worn by women participating in

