- Risk of additional clinical interventions or exams that may or may not be beneficial: Alerts of abnormal physiologic signs may prompt doctors to perform additional exams and clinical interventions. If abnormalities in physiologic signs do not correspond to developing or established clinical abnormalities this may mean additional procedures are performed without benefit. We will monitor for any substandard clinical care to participants, or participant distress caused by this and modify study protocols as necessary.
- Less than 24 hours between recruitment and consent: As noted above peripartum woman will be approached for recruitment into the study once admitted to the unit for delivery to allow monitoring to begin immediately after delivery. Due to this timeline, there will be less than 24 hours between initial approach and consent. Particularly given the high intensity time around childbirth, this exposes the women to some vulnerability in decision-making. The RA recruiting and seeking consent will be carefully trained to fully explain the risks and benefits and to ensure women understand that they will still receive current standard of care at the hospital should they decline to participate. Women indicating interest in participating will be approached again once the decision has been made for an emergency cesarean delivery. Due to potential unpredictable changes in clinical course and the development of complications that may render a woman unable to provide consent for herself, we have limited enrollment to those women who can either consent for themselves or who have a guardian available to consent for themselves. Consent via a guardian is included as monitoring critically ill women who may be unable to provide their own consent is paramount to ultimately affecting clinical outcomes

Both clinicians and peripartum women:

- Stress and anxiety related to study procedures: Post-graduate doctors may experience some stress and anxiety due to the requirement to hold the responder phone particularly given they

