**Table 1: Severe Maternal Outcomes**

Outcome	Definition/Measurement
Death	Mortality occurring at any time point after delivery and prior to discharge
Clinical based near-miss criteria	
Acute cyanosis	Blue or purple coloration of the skin or mucous membranes due to low oxygen saturation
Gasping	Terminal respiratory pattern, the breath is convulsively and audibly caught.
Oliguria	Urinary output < 30 ml/hour for 4 hours or < 400 ml/24 hours non-responsive to fluids/diuretics
Failure to form clots	Bedside clotting test or absence of clotting from the IV site after 7 minutes
Prolonged unconsciousness	Complete or near-complete lack of responsiveness to external stimuli
Cardiac arrest	Sudden absence of pulse and loss of consciousness
Stroke	Neurological deficit of cerebrovascular cause persisting $\geq 24$ hours
Uncontrollable fits	Refractory, persistent convulsions or status epilepticus
Total paralysis	Complete or partial paralysis of both sides of the body
Jaundice in the presence of pre-eclampsia	BP > 140/90 with proteinuria ( $> 1$ + dipstick in $\geq 2$ samples) and jaundice
Laboratory-based near miss criteria	
Acute severe azotemia	Creatinine $> 300$ mmol/l or $> 3.5$ mg/dl
Severe acute hyperbilirubinemia	Bilirubin $> 100$ $\mu$ mol/l or $> 6.0$ mg/dl.
Severe acute thrombocytopenia	$< 50\,000$ platelets/ml
Management-based near-miss criteria	
Use of continuous vasoactive drugs	Uninterrupted infusion of dopamine, epinephrine, or norepinephrine
Hysterectomy	Surgical removal of the uterus following infection or hemorrhage
Massive transfusion	Transfusion of $\geq 5$ units of blood
Intubation and ventilation not related to anaesthesia	Placement of an endotracheal tube or ventilation for $> 60$ minutes purposes other than anaesthesia
Dialysis for acute renal failure**	
Cardiopulmonary resuscitation	Emergency procedures including chest compressions and lung ventilation

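### SMO is read from records written by unmasked staff, and closer observation in intervention blocks may raise the recorded count; no analysis tests for this

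*Protocol*

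**What the plan says.** Protocol, Study Procedures, item 11: every 24 hours a research assistant is to "perform medical chart review on enrolled participants to assess for documentation of the occurrence of any severe maternal outcome". The same item adds the covering clinicians' daily reports, to pick up events that the chart misses. Protocol Table 2 and SAP Table 1 list the components: clinical signs, laboratory criteria and treatments. One treatment criterion is "Uninterrupted infusion of dopamine, epinephrine, or norepinephrine". Severe bradypnea or tachypnea, and shock, appear in protocol Table 2 only.

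In intervention blocks the device gives "continuous real-time transmission of oxygen saturation, respiration rate, pulse rate, temperature, motion and activity, and posture captured every 2 seconds" (Protocol, Study Intervention). Under Study Procedures, items 9 and 10, alerts carrying the abnormal value go to staff phones, and midwives are asked to tell a doctor. The protocol's risk section says: "Alerts of abnormal physiologic signs may prompt doctors to perform additional exams and clinical interventions". Control blocks have usual monitoring and record review only (item 4), at a hospital where, on the recommended frequency of observation, the protocol's background says that "such normative standards around monitoring are unattainable with current systems of physiologic monitoring".

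Neither document describes masked outcome assessment, adjudication, a testing schedule common to both arms, a rule on device readings, or an analysis of unequal ascertainment.

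**The concern.** An SMO enters the analysis only once someone has written it down. Some components will be written down under almost any level of monitoring. Others exist in the record only if someone looked, sent a sample or started a treatment. If intervention blocks bring more looking, testing or treating, the second kind can rise there without any change in the women's true condition.

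The staff cannot be masked: midwives place the sensors and hold the alert phone. The research assistants may place sensors too (item 6c), give the acceptability questionnaire (item 16) and download the device data (item 20). Aim 2 counts clinical actions after alerts as adoption, so success there is also the route by which recording in Aim 1 could become unequal.

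The reading of a null or adverse primary result is at stake. It matters during the trial as well: the DSMB is asked to look for higher SMO rates than expected (Protocol, Monitoring and Quality Assurance), and the SAP has no formal stopping rules (Interim Monitoring).

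**Working it through.** **1. Which components are exposed**

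| Components | List | What recording needs |
|---|---|---|
| Respiratory rate, shock | Protocol Table 2 only | a vital-sign measurement |
| Cyanosis, oliguria | both | bedside observation |
| Creatinine, bilirubin, platelets | both | a laboratory test |
| Vasoactive infusion, massive transfusion | both | a treatment decision |
| Hysterectomy, intubation or ventilation, dialysis | both | a treatment decision, but a major event unlikely to go unrecorded |
| Death, cardiac arrest/CPR, stroke | both | little dependence on monitoring |

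The last column is my judgement from the definitions.

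**2. The plan's own figures**

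Protocol, Sample Size: "Assuming an intraclass correlation coefficient of 0.01, the effective sample size after taking account of clustering is 633 per group". With 1,235 women per arm and 95 per block, 1235 / (1 + 95 × 0.01) = 633.3; the usual 1 + (m − 1) × ICC gives 636.6. Next: "This will allow us to detect a difference of 5.7% in the SMO rate between the two study arms", at 80% power from a baseline of 13%. At 633 per group, two-sided 0.05, power is 79.4% for 13% against 18.7%, which matches the stated 80%. For the reduction that the trial hopes for, 13% to 7.3%, power is 92.0%. The protocol gives no direction; I use the reduction below. The arithmetic reproduces, so this point concerns bias.

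**3. Illustration of unequal recording**

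Assumptions, none of them from the documents: a share s of women with SMO qualify solely through exposed components; these are documented 50% of the time in control and 90% in intervention blocks; all other SMOs are always documented; true rates are 13% and 7.3%.

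Observed rate = true rate × [(1 − s) + s × documentation].

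For s = 30%: control 0.13 × (0.70 + 0.15) = 0.1105; intervention 0.073 × (0.70 + 0.27) = 0.0708; difference 0.0397. With no true effect: 0.13 × 0.97 − 0.13 × 0.85 = 0.0156.

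| s | Control | Intervention | Observed reduction (true 5.7 points) | Power at 633 per group | Apparent harm if no effect | Chance of significant harm |
|---|---|---|---|---|---|---|
| 20% | 11.70% | 7.15% | 4.5 points | 79% | 1.0 points | 8% |
| 30% | 11.05% | 7.08% | 4.0 points | 69% | 1.6 points | 14% |
| 50% | 9.75% | 6.94% | 2.8 points | 44% | 2.6 points | 31% |

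Without the bias, power is 92% and the chance of significant harm is 2.5%.

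**4. Sensitivity to the assumptions**

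- If 13% is the documented control rate, the intervention rate is 7.3% × (1 − 0.1s)/(1 − 0.5s). The observed reduction is then 5.1, 4.7 or 3.8 points.
- If only 85% of an intervention block is monitored (the protocol's consent assumption), documentation there is 0.85 × 90% + 0.15 × 50% = 84%. The reductions are 4.6, 4.1 and 3.0 points; the apparent harms are 0.9, 1.3 and 2.2.
- As a single ratio r of recording, intervention to control, with the control rate held at 13%: r of about 1.12 cuts power from 92% to 80%, about 1.30 cuts it to 50%, and 0.13 / 0.073 = 1.78 makes the recorded rates equal.
- If the SAP's 1,266 are actual women over 26 blocks, the design effect is 1 + (633/13 − 1) × 0.01 = 1.477 and the effective size is 633 / 1.477 = 429 per arm. Power is 79% at r = 1.0, 66% at 1.1 and 51% at 1.2.

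**The case against.** A reader might infer that the design adds tests and treatment in one arm. It does not: none is mandated, and the response to an alert is left to the covering doctor under the hospital's usual standards (Study Procedures, item 9). Only a likely difference in intensity can be claimed.

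A reader might also infer that readings every 2 seconds feed most of the composite. They do not. The device measures no urine output, creatinine, bilirubin or platelets. Cyanosis is defined by visible colour, and neither alert table includes oxygen saturation. SAP Table 1 omits the two criteria set directly by vital-sign values. If that list governs, what remains is mainly the indirect route through discretionary care.

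A third tempting inference is that the bias must run against the intervention. Earlier care might avert transfusion or dialysis, and staff who rely on the device might chart fewer manual observations. The documents do not settle the net direction.

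Some protection exists. The 24-hour reports are a second source, though clinicians who know the block write them too. Charted vital signs are already extracted (item 12). The DSMB is asked whether higher rates are related to the intervention, not to take them as harm. Events count to discharge while monitoring lasts 24 hours, and the SAP analyses all eligible women in a block; both dilute the effect.

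These points limit the claim. They do not equalise recording between arms, and they supply no analysis that would show whether it was equal.

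**Conclusion.** The concern holds in limited form. Recording of some SMO components may be more complete in intervention blocks, this can mask a benefit or mimic harm, and nothing in the plan would reveal it. The 4.5, 4.0 and 2.8 points, and the 1.0, 1.6 and 2.6 points of apparent harm, rest wholly on the assumed 50% and 90% documentation and on s; they show that a moderate imbalance would matter, not that one exists. It does not follow that the primary composite should be replaced, nor that device-derived values should be barred: if these replace manual charting, a bar would undercount events in the intervention arm. Uncertain direction is a reason for a prespecified sensitivity analysis.

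**What to change.** 1. Reconcile protocol Table 2 and SAP Table 1 into one component list, and keep that composite as primary.
2. In SAP Aim 1, prespecify a sensitivity analysis with the same model on the components least dependent on monitoring: death, cardiac arrest/CPR and stroke. Add a second version with hysterectomy, intubation or ventilation, and dialysis. Leave massive transfusion out of both, since it is among the exposed components.
3. Tabulate each component by arm, alongside charted vital-sign documentation and, where available, laboratory testing.
4. Apply the same extraction sources to all eligible women in both arms. Item 11 reviews enrolled participants, whereas SAP Aim 1 also counts women who declined, were missed or were not enrolled. Flag any SMO that rests only on a device-derived reading, and show the result with and without it.
5. State that if the primary and restricted results disagree in direction, the report will not claim harm or no effect from the primary alone.

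The cost is SAP wording, two further model fits and some fields on the abstraction form. Whether the form already holds each component separately cannot be checked, because protocol Appendix 1 is not among the documents. The statistical downside is that the restricted composite has fewer events and wider intervals, so it informs the reading of the primary result and does not replace it.

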Aim 1: The primary outcome measure is the rate of severe maternal outcome (SMO). This is a composite measure drawn from WHO near miss morbidity criteria (Table 2). Secondary outcome measures include: the maternal mortality rate, maternal near miss rate and case fatality rates for postpartum hemorrhage, hypertensive disease and sepsis – the three most common causes of maternal death. The event rates for both primary and secondary outcomes will be compared using logistic regression models with the Generalized Estimating Equations approach to take into account of patients within clustering (due to time blocks). Exploratory analyses will be used to determine if a) the intervention is more powerful in certain subgroups of women and b) if any provider was consistently different in maternal outcomes regardless of intervention. The interaction between study arm and comorbidities (HIV, hypertension, pulmonary, cardiac or kidney disease, malaria) or provider will be tested in the logistic regression models. Subgroup effects will be reported if there is strong evidence of heterogeneity of intervention effect

Aim 2: We will apply the RE-AIM model to conduct a quantitative evaluation of the implementation of the intervention used in Aim. Table 4 describes the primary metrics to be measured and data sources from which it will be collected.

RE-AIM Implementation Science Framework ^{37,38}			
Metric	Dimension	Study Measure	Data source
Reach	Proportion of target population that participated in the intervention	
 Percent of women with successful placement of biosensor after delivery Total length of time for monitoring over 24hrs postpartum Percent of women participating in monitoring for 24 hrs 	
 Physiologic data from biosensor Time of delivery from chart records & theatre log books
Efficacy	Success rate if implemented as in guidelines	
 Percent of women with HR, BP, RR and Tp available at least every 4 hours for 24 hrs after delivery Percent of appropriate SMS alerts sent 	
 Physiologic data from biosensor RA review of mobile phones for SMS alerts and time of receipt

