##### Primary outcomes

- Composite of severe maternal outcome – one or more of the following outcomes represented in Table 1

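### Two laboratory limits in the primary composite carry wrong units: the creatinine row contradicts itself about 1,000-fold, and the platelet limit, read literally, would capture practically no case

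*Protocol*

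**What the plan says.** The protocol (Biostatistical Analysis, Aim 1) makes the SMO rate the primary outcome and defines it through Table 2. The SAP (Primary outcomes) defines it as "Composite of severe maternal outcome – one or more of the following outcomes represented in Table 1". Meeting a single row is therefore enough to make a woman a case.

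Protocol Table 2 has three laboratory rows:
- creatinine: "Creatinine > 300 mmol/l or > 3,5 mg/dl"
- bilirubin: "Bilirubin > 100 µmol/l or > 6.0 mg/dl"
- platelets: "<50 000 platelets/ml"

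SAP Table 1 repeats all three with the same numbers and units, including per ml in its row for "Severe acute thrombocytopenia". Neither table has a footnote, reference range or second unit for platelets.

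On data capture, Protocol Study Procedures item 11 says: "Every 24 hours a research assistant will perform medical chart review on enrolled participants". The purpose is to find documented SMOs listed in Table 2, with the clinicians' 24-hour reports as a second source. Item 12 refers to a chart review form (Appendix 1), and the SAP (Data sources) says that chart review data are entered into REDCap. The form itself is not in the text available here.

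**The concern.** These are case-defining limits in the primary endpoint. The creatinine row gives one limit in two units that cannot both be right. The platelet row gives one limit in one unit, and that limit lies far below any count that a laboratory is likely to report.

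Two things are at stake. If the platelet limit is applied as printed, a woman who qualifies on platelets alone is counted as event-free. If some research assistants read the limit as per µl and others do not, the same laboratory report is classified in two ways, and the tables give no basis for settling which is right.

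**Working it through.** **Inputs.** The three limits come from Protocol Table 2 and SAP Table 1. The molar masses (creatinine 113.12 g/mol, bilirubin 584.66 g/mol) are physical constants that the documents do not give. The limits are definitions, so there is no derived figure to reproduce. The bilirubin row serves as a check on the method.

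**Bilirubin, the row that reconciles.** 6.0 mg/dl = 60 mg/L; 60 / 584.66 = 0.1026 mmol/l = 102.6 µmol/l, against a printed 100 µmol/l. In reverse, 100 µmol/l = 5.85 mg/dl. The gap of about 3% is rounding. The micro sign is intact in this row in both documents, so a character lost in text conversion is an unlikely explanation for the other two rows.

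**Creatinine.** 3.5 mg/dl = 35 mg/L; 35 / 113.12 = 0.309 mmol/l = 309 µmol/l. The printed SI limit is 300 mmol/l, and 300 / 0.309 ≈ 970. In reverse, 300 mmol/l × 113.12 / 10 = 3,394 mg/dl, against a printed 3.5. Replacing mmol with µmol brings the two limits within about 3% (309 / 300 = 1.03), the same rounding gap as for bilirubin. This contradiction is visible within the row itself.

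**Platelets.** 50,000 per ml / 1,000 = 50 per µl = 0.05 × 10⁹/L. The documents give no range of counts, so I assume 1 to 400 × 10⁹/L:

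| Count (× 10⁹/L) | Per ml | Multiple of printed limit |
|---|---|---|
| 1 | 1,000,000 | 20 |
| 10 | 10,000,000 | 200 |
| 20 | 20,000,000 | 400 |
| 50 | 50,000,000 | 1,000 |
| 150 | 150,000,000 | 3,000 |

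No count in the assumed range falls below the printed limit. If per µl was intended, the limit would be 50 × 10⁹/L, exactly 1,000 times the printed one.

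**Possible effect on power.** The Protocol's Sample Size section gives 1,235 women per group, about 95 per block, an intraclass correlation of 0.01, an effective 633 per group, a 13% baseline rate and a detectable difference of 5.7 points. The effective size reproduces: 1,235 / (1 + 95 × 0.01) = 633.3 (636.6 with 94 in place of 95).

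I use the normal approximation for two proportions:

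Power = Φ{ [ |p₁ − p₂| − 1.96 √(2p̄(1 − p̄)/n) ] / √([p₁(1 − p₁) + p₂(1 − p₂)]/n) }

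At n = 633 this gives 79.4% for an increase from 13% to 18.7%, which matches the stated 80%, and 92.0% for a reduction to 7.3%.

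Now assume that a share f of SMO cases in each arm qualifies on platelets alone and is lost, so that both rates are multiplied by (1 − f). The documents give no value for f; the range is mine.

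| f | Control rate | Power, reduction | Power, increase |
|---|---|---|---|
| 0 | 13.0% | 92.0% | 79.4% |
| 1% | 12.9% | 91.7% | 78.9% |
| 5% | 12.35% | 90.5% | 76.9% |
| 10% | 11.7% | 88.7% | 74.3% |

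Even at 10% the loss is 3 to 5 points of power.

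**The case against.** The strongest case for leaving this as a trivial correction has four parts.

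- **The intended platelet unit is not in the documents.** Per µl is an inference from the implausible printed limit and from the creatinine row beside it. This stands: the sponsor has to confirm the unit. It does not rescue the printed limit.
- **Literal application is not shown.** Case finding is by a person reading charts and clinicians' reports, not by a program converting laboratory values. An assistant may already read the limit as per µl, or record a diagnosis that a clinician wrote down. This also stands. A reader might infer that the platelet component cannot be met or that events have certainly been lost; the documents do not support that without the chart review form.
- **The creatinine row still works.** Its limits are joined by *or*, and the mg/dl limit identifies cases correctly. The remaining risk is for results reported in SI units, which the assistant would have to convert. The documents do not say which units the hospital laboratory uses.
- **The effect is probably small.** Thrombocytopenia is one of 22 rows in Protocol Table 2 and one of 20 in SAP Table 1, and a woman with severe thrombocytopenia may qualify on another row as well. This stands, and it limits the weight of the point.

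A reader might also infer that the laboratory rows were mis-transcribed from their sources. That cannot be tested: the cited criteria are not available here, the units may have been carried over as printed there, and the bilirubin row is correct.

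**Conclusion.** The concern holds for the units of two rows. The creatinine error is demonstrable from the row itself and is about 1,000-fold, but a usable limit stands beside it. The platelet limit is implausible as printed and has no alternative. Read literally, it would in practice capture no case over an assumed range of 1 to 400 × 10⁹/L. The factor of 1,000 for platelets depends on per µl being the intended unit.

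The consequence is possible loss of events and inconsistent coding of the primary outcome. A reader might infer bias between the arms, but the wording is identical for intervention and control blocks and nothing in the documents suggests that it would be read differently in one of them. The share of SMO events at risk is not stated. Under assumed shares of 1% to 10%, power for a 5.7-point reduction falls from 92.0% to between 91.7% and 88.7%. The point is worth correcting because it concerns a primary-outcome definition and the correction is cheap; it does not threaten the trial.

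**What to change.** - In Protocol Table 2 and SAP Table 1, change the SI unit for creatinine to µmol/l.
- In both tables, change the platelet unit to per µl (50 × 10⁹/L), after the sponsor has confirmed that unit against the near-miss criteria it cites.
- Check how both limits are worded in the chart review form (Appendix 1) and coded in REDCap, and tell the research assistants which units apply.
- If charts have already been abstracted, re-check the recorded platelet values against the confirmed limit in both arms, without reference to arm where possible. Review creatinine results reported in SI units at the same time.

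The cost is two rows in each of two tables, a check of the form and its coding, and, if abstraction has begun, a second look at recorded platelet and SI-unit creatinine values. The design, sample size and analysis model do not change.
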